University of Wisconsin-Madison

Study #: 2017-0755

IRB Approval Date: 7/17/2017

**COMBINATION VERSUS MONOTHERAPY WITH ALPHA-BLOCKERS AND
ANTICHOLINERGICS FOR THE RELIEF OF URINARY STENT SYMPTOMS - A
RANDOMIZED CONTROL TRIAL**

Principal Investigator: [name]

Co-Investigator: [name]; [name]; [name]

University of Wisconsin-Madison, School of Medicine and Public Health, Department of Urology

BACKGROUND AND SIGNIFICANCE

Ureteral stents are used to relieve acute or chronic obstruction of the upper urinary tract, or used as a prophylactic measure following instrumentation or surgery involving the ureter. Ureteral stents work by re-establishing or maintaining patency of the ureter in conditions of obstruction or injury. Stents passively dilate the ureter, allowing urine to flow both through and around the stent, and are indicated when there is ureteral obstruction with or without renal insufficiency, secondary to nephrolithiasis, malignancy, or other pathologic processes. Additionally, they can be used as a prophylactic measure after endoscopic procedures involving the ureter, or surgical repair of the ureter such as in ureteral anastomoses.

Unfortunately, despite their use since the late 60's, stent related symptoms are common in patients after stent insertion and continue to be a challenge to manage. Overall quality of life is impaired in 45% - 80% of patients with ureteral stents in place ¹. Stent related symptoms occur in up to 80% of patients following stent insertion. These include: storage urinary symptoms such as urinary frequency, urgency, nocturia, dysuria, hematuria, stent colic (flank/SP pain), and incomplete emptying or urinary incontinence. To date, various methods have been investigated and employed in an effort to alleviate these symptoms, from various stent designs to pharmacotherapy. With respect to pharmacologic management of stent symptoms, various agents have been investigated, including intravesical pharmacologic therapy ², periureteral injection of botox ³, selective alpha-1 blockers ⁴, and anticholinergic agents ⁵.

University of Wisconsin-Madison

Study #: 2017-0755

IRB Approval Date: 7/17/2017

There are several studies documenting the evidence supporting the use of alpha-blockers to reduce stent discomfort, including two recent meta-analyses^{4,6}. These analyses demonstrated a significant benefit for using either tamsulosin or alfuzozin in relieving symptoms. However, only a few studies have assessed the efficacy of anticholinergic agents in this context, despite the theoretical and anecdotal benefits of this class of drugs. The available literature on anticholinergic therapy for stent symptom relief do show benefits, e.g. in one study, tolterodine ER showed symptom improvement over placebo⁷. Data on combination therapy with both agents is even more limited and show mixed results, from no advantage to modest benefits in the combination arm^{8,9}. There is also evidence that suggests tolterodine ER does not achieve maximum benefit upon initiation of the medication. Kaplan et al. found no difference in urinary symptoms between placebo and tolterodine ER at 1 week, however by week 4 of medication therapy tolterodine ER was significantly better than placebo at improving urinary symptoms.¹⁰ There is no available literature on the effect of starting tolterodine ER prior to surgery to give maximum benefit of the medication prior to placement of a ureteral stent.

We plan to design our study in a manner that will address some of the methodological weaknesses of the aforementioned studies, and use the most commonly used alpha-blocking and anticholinergic agents and dosing: tamsulosin 0.4mg PO OD and tolterodine ER 4mg PO OD, respectively.

OBJECTIVES AND HYPOTHESIS:

University of Wisconsin-Madison

Study #: 2017-0755

IRB Approval Date: 7/17/2017

We aim to show that the addition of Tolterodine ER to Tamsulosin will provide added benefits in ameliorating stent related symptoms in patients who have had unilateral placement of a ureteral stent for urolithiasis. This objective will be assessed by determining the mean difference in the urinary symptom index domain of the USSQ (the Urinary Stent Symptom Questionnaire), which is a validated tool used to assess stent symptoms¹. We felt that a 15% further decrease in the index score in the experimental group, compared to the control group would represent a clinically significant improvement in urinary symptoms, based on the prior studies evaluating lower urinary tract symptoms in patients with stents. We hypothesize that combination therapy with Tamsulosin and Tolterodine ER will yield greater symptom relief than tamsulosin alone. In addition, we hypothesize that a longer duration of treatment of Tolterodine ER, 2 weeks prior to insertion of the stent, will yield greater symptom relief than initiation of Tolterodine ER after stent placement or tamsulosin alone.

RESEARCH DESIGN AND METHODS:

This is a prospective, double blind, randomized control trial.

STUDY SITE

This study was originally planned to take place at UW Health, Meriter Health Sciences, Vista Medical Center East and University of Manitoba. Three of the sites were unable to recruit patients to the study and have dropped out of the study: Meriter Health Sciences, Vista Medical Center East and University of Manitoba. Thus, the study was amended in 2014 to be a single site study conducted only at the UW Health.

University of Wisconsin-Madison

Study #: 2017-0755

IRB Approval Date: 7/17/2017

The study site will obtain an IRB approval prior to recruiting any patients.

1. UW hospitals and clinics. Department of Urology, Madison, WI.
 - Study coordinator – [name], & [name]

STUDY ACTIVITIES

Patients who will be undergoing urinary stent insertion during the management of renal or ureteral stones, or other conditions requiring endoscopy will be randomized into the combination or monotherapy arm, based on a computer generated randomization scheme, and will be enrolled into the study arm in a blinded manner. The study is intended to be double-blinded. The drug kit will be linked to the randomization number and both the investigator and patient will thus be blinded to the treatment. All patients will be required to provide a signed informed consent, which outlines the differences in the two treatment arms and study objectives. Patients will be provided the corresponding pills in pre-filled vials, based on their group assignment. Initially, the study used a 7-day treatment regimen. Patients in the monotherapy arm were given a set of Tamsulosin and placebo pills, while the combination therapy arm were given a set of Tamsulosin and Tolderodine ER, with sufficient quantities for 7 days. Pill counts were obtained at the end of the follow-up period to ensure compliance. All patients enrolled into the study were asked to complete the USSQ prior to stent insertion to serve as a baseline assessment of urinary symptoms, and again at 24 hours, 5 days after stent insertion and post stent removal. In the 7-day regimen, 80 patients were enrolled and completed the study (15 patients enrolled but withdrawn, 95 patients in total).

University of Wisconsin-Madison

Study #: 2017-0755

IRB Approval Date: 7/17/2017

The data analysis shows no benefit from being on combination therapy likely secondary to the short duration of therapy.

In 2014, a change of protocol was approved that extended the study treatment to 21 days. Patients will start the study medication 2 weeks prior to their surgery date and continue for the 1 week duration of the stent. Patients in the monotherapy arm will be given a set of Tamsulosin and placebo pills, while the combination therapy arm will be given a set of Tamsulosin and Tolderodine ER, with sufficient quantities for 21 days. Pill counts will be obtained at the end of the follow-up period to ensure compliance. All patients enrolled into the study will complete the USSQ at baseline prior to starting medication to serve as a baseline assessment of urinary symptoms, prior to stent insertion, and again at 24 hours, 5 days after stent insertion and post stent removal. The patients will have the stent removed in 7 days, which will conclude the study period. If the stent needs to be removed sooner, it will be arranged as per current protocol. Early termination is only relevant if the 5 day USSQ is not completed. In the 21-day regimen, 106 patients are planned to be enrolled. Thus, a total of 201 patients, to see if there is a difference with the longer duration of medication treatment. Subjects have been enrolled on this 21-day regimen since 10/29/2014, and all new subjects use this regimen.

STUDY POPULATION

The key participants of this study will be male and female adult patients with kidney or ureteral stones, or other conditions, requiring unilateral or bilateral ureteral stent placement, either before or after a surgical intervention. Specifically, the post-operative

University of Wisconsin-Madison

Study #: 2017-0755

IRB Approval Date: 7/17/2017

stent patients will include those who have undergone ureteroscopy, percutaneous nephrolithomy or extracorporeal shock-wave lithotripsy.

INCLUSION CRITERIA

Patients with unilateral or bilateral ureteral stent placement for urolithiasis are candidates for enrollment. These include: patients who have undergone ureteroscopy for renal or ureteral calculi, percutaneous nephrolithotomy (PCNL), shock-wave lithotripsy (SWL), or other conditions requiring stent placement post operatively, or for relief of pain or obstruction.

EXCLUSION CRITERIA

Candidates will be excluded from the study if ANY of the following apply:

1. Pre-existing LUTS
2. Active UTI
3. Contraindication to anticholinergic medication
 - a. Prior hypersensitivity or allergy to tolterodine
 - b. Patients with severe hepatic impairment (Child-Pugh Class C)
 - c. Patients with uncontrolled close (narrow) angle glaucoma
 - d. Patients with urinary retention
4. Current anticholinergic use
5. Chronic pelvic pain syndromes (e.g. acute/chronic prostatitis, interstitial cystitis)
6. Females who are pregnant or nursing
7. Under 18 years of age
8. Any patients unable to provide informed consent

PATIENT SCREENING AND RECRUITMENT

Potential subjects will be identified by the surgeon or study coordinator either at the time ureteroscopy, PCNL or stent placement is scheduled. These subjects will be screened for inclusion/exclusion criteria by reviewing their medical record. A waiver of patient screening is requested in the current application. If inclusion/exclusion criteria are met, the surgeon will ask the patient if he or she is interested in talking with a study team member for a study that he or she is eligible. Once the patients' permission is obtained, a member of the research team will approach the patient for enrollment. Subjects will be recruited by verbal communication by the principal or co-investigators, or by a research coordinator. The patient must consent to participate as evidenced by the signed, study-specific, IRB-approved informed consent form before any study specific data may be collected and recorded.

We have requested a waiver of patient screening. We believe that the screening process will not pose more than minimal risks to subjects or adversely affect the rights and welfare of the subjects. The screening process only consists of reviews pre-existing data. No patient care or outcomes are affected as a result of screening. The surgeon or study coordinator will only review the medical record that is relevant for inclusion/exclusion criteria. No data will be collected in this phase. The exclusion criteria for the current study include pre-existing LUTS, active UTI, contraindication to anticholinergic medication, current anticholinergic use, chronic pelvic pain syndromes, pregnant females, and under 18 years of age. In the Urology clinic, a significant amount of patients who undergo stone

University of Wisconsin-Madison

Study #: 2017-0755

IRB Approval Date: 7/17/2017

surgeries may have LUTS, active UTI, or currently taking anticholinergic medication. Consent without pre-screening will create a significant dropout rate. Thus, the study could not practicably be carried out without the waiver of screening.

Once appropriate informed consent has been obtained, a complete medical history including a detailed urologic history will be completed. The subject will be randomized to one of the two arms (tamsulosin + placebo versus tamsulosin + tolterodine) using a computerized randomization scheme.

STUDY DRUG/INTERVENTION

The study drugs of interest are Tamsulosin and Tolterodine ER, both of which are routinely used in urology. The UW pharmacy will supply the study drugs and placebo. Each of the study drugs and placebo will be provided in standard drug vials. Under the original, 7-day study treatment regimen, each vial contained 7 pills each. In 2014, the study was amended to add a 21-day treatment regimen. This replacement study will use only the 21-day treatment regimen, and the drug vials will contain 21 pills each. The placebo capsule will be similar in color and appearance to the Tolterodine capsule, and will be provided by the UW pharmacy. Patients may continue to use any prior medications concurrently with either of the study drugs, and no washout period is necessary.

TAMSULOSIN

University of Wisconsin-Madison
Study #: 2017-0755
IRB Approval Date: 7/17/2017

Tamsulosin is a selective α_{1a} -blocker (Flomax™), generic since 2009. It is an antagonist of α_1 -mediated contraction of prostate, bladder and proximal urethral smooth muscle, and as such, reduces urethral pressure and resistance, bladder outlet resistance, bladder hyperactivity, and consequently LUTS. Its adverse effects include headache, dizziness, asthenia, nasal congestion, retrograde ejaculation, and a rare reversible condition known as floppy iris syndrome, which is only relevant if patients are undergoing cataract surgery.

TOLTERODINE ER

Tolterodine ER is an anticholinergic (antimuscurinic) agent, which is used as one of the first line agents for detrusor overactivity. It is given as once-daily dosing for overactive bladder symptoms, and even used in BPH patients exhibiting bladder symptoms. Its side-effects include xerostomia, xerophthalmia, gastroparesis, constipation, drowsiness, acute urinary retention, but unlike other drugs of this class, e.g. oxybutynin, tolterodine ER causes little to no cognitive impairment due to its larger molecular weight which precludes crossing of the BBB.

SAFETY AND MONITORING

Regular inquiries of study flow, pertaining to patient recruitment, randomization, patient compliance (with medication and completing questionnaires) and adverse events will be scheduled to occur after the first week and subsequently every two weeks during the active patient enlistment phase. Any adverse events/side effects will be monitored as per

University of Wisconsin-Madison

Study #: 2017-0755

IRB Approval Date: 7/17/2017

standard protocol in clinical use. Patients will be instructed to report any untoward reactions to the study drugs to the urology clinic or on-call urology staff.

No significant adverse events are anticipated with either of the study drugs, as they are routinely used in everyday urology practice. The patient will report side effects if and when they occur; the drug will be stopped if continuation is deemed inappropriate. Any adverse events or unanticipated problems will be recorded and the offending drug will be stopped, and the patient counseled accordingly. If a patient has side effects that precludes their ongoing participation in the study, they will be withdrawn and considered a study drop-out. All measures will be in effect to prevent breaches of confidentiality and/or emotional upset.

Patients are instructed to contact their treating surgeon if they have symptoms that may require placing the stent or having surgery sooner than expected. The surgeons who perform these procedures are also members of the study team, and will ensure that all patients' clinical care will not be influenced due to study participation. We confirm that study participation will not delay needed clinical care in the event that an enrolled subject requires stent placement sooner than anticipated. We will only include patients whose stent placement will not be delayed as a result of study participation. If the patient has the stent placed in the interim or has discontinued medications, he or she will be excluded from the study.

University of Wisconsin-Madison

Study #: 2017-0755

IRB Approval Date: 7/17/2017

STATISTICAL ANALYSIS & POWER CALCULATIONS:

In 2014, a change of protocol was approved that extended the study treatment to 21 days. Our sample size calculation in the 21-day regimen was based on the recommended sample size calculations by the original developers of the USSQ ¹. The authors' calculations were based on the results of their validation studies that compared mean domain score and standard deviation differences between stented and control patients, using a 2-tailed test ($p < 0.05$). The percentage change (15%) translates to an absolute change in score by 4 points. Additionally, we extrapolated data from a recent meta-analysis evaluating the efficacy of tamsulosin to relieve stent related symptoms, which showed a mean standard deviation of 6.5 points between the tamsulosin and placebo arm ⁴ to confirm the previous authors' sample size. With an expected decrease of 4 points with the combination therapy, and an assumption of similar standard deviation (6.5), a two-tailed t-test ($p = 0.05$) and power of 0.80, our calculation yielded 43 patients per arm. Given the relatively similar numbers from the two calculations, we opted to use the more conservative sample size of 53 patients per arm as the data collection endpoint.

We are assessing for both an absolute and relative change in the USSQ scores.

1. We will be assessing for a relative change of 4 actual points (which translates to a 15% change, as per Joshi et al's validation study) within each group from immediately post stent insertion at 24 hours compared to day 5.
2. We will also assess for a change in scores between groups, i.e. comparing the mean intra-group score change as described in 1 (i.e., immediately post stent insertion at 24 hours compared to day 5).

University of Wisconsin-Madison
Study #: 2017-0755
IRB Approval Date: 7/17/2017

The questionnaire responses will be analyzed using cross tabulations and descriptive statistics to assess differences between groups. Paired *t*-tests will be used to assess within-group change in scores from the USSQ (comparison between post-op, i.e. at 48 hours, and day 5) and other discriminant properties. *T*-tests will be used to assess inter-group score changes.

The intent-to-treat principle will be employed in the event subjects have to withdraw from their assigned group, although this is not expected given that both treatment medications are used extensively in urology, and both treatment regimens are occasionally employed based on anecdotal physician experience.

DATA SECURITY:

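### The hypothesis that tolterodine started 2 weeks before the stent beats tolterodine started after it has no concurrent randomised comparison, no planned analysis and no power calculation; delete it or label it exploratory

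*Combined protocol and SAP*

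**What the plan says.** The main objective in Objectives and Hypothesis is to show that adding tolterodine ER to tamsulosin helps. A further hypothesis concerns timing: tolterodine ER "2 weeks prior to insertion of the stent, will yield greater symptom relief than initiation of Tolterodine ER after stent placement", and also more relief than tamsulosin alone.

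Study Activities describes two regimens in sequence. Under the first, patients received 7 days of drug; 95 enrolled, 15 withdrew and 80 completed. Of this cohort the text says: "The data analysis shows no benefit from being on combination therapy likely secondary to the short duration of therapy". A change approved in 2014 lengthened treatment to 21 days, starting two weeks before surgery in both arms, with 106 patients planned. The section then adds the cohorts: "Thus, a total of 201 patients, to see if there is a difference with the longer duration of medication treatment". It also says: "Subjects have been enrolled on this 21-day regimen since 10/29/2014, and all new subjects use this regimen".

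Patient Screening and Recruitment gives the allocation: "The subject will be randomized to one of the two arms (tamsulosin + placebo versus tamsulosin + tolterodine". Study Drug/Intervention says: "This replacement study will use only the 21-day treatment regimen".

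Statistical Analysis & Power Calculations plans paired t-tests within groups and t-tests between groups on the post-stent change in score to day 5. Its only power calculation is for a 4-point benefit of combination therapy, with 53 patients per arm adopted for the 21-day regimen.

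**The concern.** The plan states a hypothesis about start time, but nobody is randomised to start time. In the current regimen both arms begin two weeks before surgery, so a later-start tolterodine group can come only from the earlier 7-day cohort. The statistical section does not say whether or how that cohort would be used.

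Without a written rule, a difference between the 21-day and 7-day regimens could be reported as an effect of early tolterodine. It could equally reflect calendar period, longer tamsulosin or a different mix of patients. The text linking the 201 total to the duration question makes that reading easier, as does the attribution of the 7-day result to short treatment.

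**Working it through.** **What each limb has behind it**

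- Tolterodine plus tamsulosin versus tamsulosin alone, 21-day regimen: randomised, with a planned t-test and a sample size.
- Tolterodine started two weeks early versus after the stent: no randomised contrast, no named test and no power calculation.

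**The plan's own figure.** Inputs from the statistical section are difference 4, SD 6.5, two-sided 0.05 and power 0.80.

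n per arm = 2 × [6.5 × (1.960 + 0.842) / 4]² = 41.4, so 42 by normal approximation. The t-test solution is 42.43, which rounds up to the stated 43. It sizes combination versus monotherapy only. At the adopted 53 per arm, SE = 6.5 × √(2/53) = 1.263 and power for 4 points is 0.886 (0.881 by t-test).

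**What a cross-regimen comparison would estimate.** Let d21 and d7 be the tolterodine effects in the two regimens, e the period effect, t the effect of longer tamsulosin and c the case-mix effect.

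- Combination 21-day minus combination 7-day = (d21 − d7) + e + t + c. All the confounders remain.
- Arm-by-regimen interaction, the difference between the two randomised differences = d21 − d7, provided e, t and c are additive and so cancel between arms. If any of them changes the tolterodine effect, it does not cancel.

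The documents show that these terms are not idle. The regimens are sequential. Tamsulosin went from 7 to 21 days in both arms. Safety and Monitoring admits only patients whose stent will not be delayed by participation and excludes those stented in the interim.

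**Illustrative precision.** Assumptions: SD 6.5 applies to the analysed score (the plan does not give an SD for the change); the 80 completers split 40/40 (split not given); the 21-day arms supply 53 each or, at the 7-day completion rate, 53 × 80/95 = 44.6, taken as 45.

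- Interaction, 53 per arm: SE = 6.5 × √(2/53 + 2/40) = 1.925; power for 4 points = Φ(4/1.925 − 1.96) = 0.547; detectable at 80% power = 2.80 × 1.925 = 5.4 points.
- Interaction, 45 per arm: SE = 6.5 × √(2/45 + 2/40) = 1.998; power = Φ(4/1.998 − 1.96) = 0.517; detectable 5.6 points.
- Range for SD 5 to 8: power 77% to 39% with 53 per arm, 74% to 37% with 45.
- Direct combination contrast, 53 v 40: SE = 6.5 × √(1/53 + 1/40) = 1.361; nominal power for 4 points = 0.836. Size is not its weakness. If start time had no effect, an assumed between-period drift of 1 point would raise its false-positive rate from 5% to 11%, and 2 points to 31%.

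So the contrast with nominal power is confounded, and the one that removes additive confounding is imprecise.

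**The case against.** The strongest reply is that this is half of a secondary hypothesis. The objective, the randomisation and the sample size all concern adding tolterodine to tamsulosin within the 21-day regimen, and the document does not propose pooling the cohorts or testing across them. That stands, and it limits the seriousness of the point. It does not remove a predicted result that the design cannot deliver.

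Three stronger readings are tempting, and the documents do not support them.

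- *That all 201 patients will be analysed together.* The total is 95 + 106, including the 15 withdrawals. It can be read as cumulative accrual, and no pooled analysis is described.
- *That the regimen was lengthened because the 7-day result was null, so any comparison with it is biased towards longer treatment.* The document reports both the null result and the 2014 change, but it does not date the analysis or say that it prompted the change. Background and Significance gives a separate reason for an early start: a cited study in which tolterodine ER differed from placebo at week 4 but not at week 1. The bias is a conditional caution, and its size would depend on an assumed true effect, so no figure is offered.
- *That the moved baseline questionnaire confounds the planned analysis.* It did move, from before the stent to before medication, but the planned change score does not use it. It matters only if someone adjusts for baseline.

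The precision figures also rest on an assumed split and SD. The sponsor may be able to use the actual values, so these figures do not belong in the protocol.

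**Conclusion.** The point holds for one limb only. The claim that early tolterodine beats tolterodine started after the stent has no concurrent randomised comparison, no specified analysis and no power. The sole possible comparator, the 7-day cohort, differs in period, tamsulosin duration and selection; that it began dosing at stent placement is itself an assumption.

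Under the stated assumptions, the least confounded available contrast has little better than even power for the plan's own 4-point target.

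A reader might infer that the trial's main conclusion is compromised. It is not: the randomised comparison within the 21-day regimen, which also serves the tamsulosin-alone limb, is untouched, with about 88% power for 4 points at 53 per arm (about 83% at 45, normal approximation). The change should be made, but it concerns what may be concluded, not whether the trial works.

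**What to change.** 1. In the statistical section, state that the confirmatory analysis is the randomised comparison of the two arms within the 21-day regimen. In Study Activities, present 201 only as cumulative accrual. Report the 7-day result separately, without pooling.
2. In Objectives and Hypothesis, delete the limb on starting tolterodine after stent placement, or label it exploratory and non-randomised.
3. If the limb is kept and the 7-day data are available to this replacement study, which the document does not say, record when 7-day dosing began. Estimate the limb as the arm-by-regimen interaction with a 95% confidence interval, not by comparing the two combination arms directly. Use the same score in both regimens; the statistical section gives the early time point as both 24 and 48 hours, and that must be reconciled first.
4. State the limits beside the estimate: it removes only additive period and tamsulosin-duration effects; it assumes that neither these nor case mix modifies the tolterodine effect; and, if the regimen was changed in the light of the 7-day result, it may be biased towards longer duration.

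The cost is wording in three sections and, if the limb is kept, one exploratory regression term in a plan that otherwise uses t-tests. No new patients are needed, and the 53 per arm stays. The downside is a weaker, openly exploratory duration claim, or none.

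### In the 21-day regimen both arms take tamsulosin, but the written rules let a patient already on an alpha-blocker enrol and keep taking it

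*Combined protocol and SAP*

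**What the plan says.** All references are to the Combined protocol and SAP.

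- **Dose.** Background and Significance says the study will use "the most commonly used alpha-blocking and anticholinergic agents and dosing: tamsulosin 0.4mg PO OD".
- **Arms and duration.** Study Activities and Study Drug/Intervention give tamsulosin to both arms for 21 days: two weeks before surgery and one week with the stent. Only the second capsule differs: "The placebo capsule will be similar in color and appearance to the Tolterodine capsule".
- **Prior medication.** Study Drug/Intervention: "Patients may continue to use any prior medications concurrently with either of the study drugs, and no washout period is necessary".
- **Drug-related exclusions.** Exclusion 3 covers contraindications to anticholinergics, including "Prior hypersensitivity or allergy to tolterodine" (3a). Exclusion 4 is "Current anticholinergic use". No exclusion names tamsulosin or alpha-blockers.
- **Restated list.** Patient Screening and Recruitment again names only the anticholinergic class: "contraindication to anticholinergic medication, current anticholinergic use, chronic pelvic pain syndromes, pregnant females".
- **Indirect restrictions.** Exclusion 1 covers existing LUTS, 3d is "Patients with urinary retention", and 5 covers chronic pelvic pain, including prostatitis.
- **History.** After consent and before randomization, "a complete medical history including a detailed urologic history will be completed".
- **After enrolment.** Under Safety and Monitoring, a drug is stopped when a reported side effect calls for it, and a patient who cannot continue becomes a drop-out.

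**The concern.** The plan guards against doubling up on one study drug class and not on the other. A patient on an anticholinergic is excluded, and so is one allergic to tolterodine, which only one arm receives. Tamsulosin, which both arms receive, has neither protection, and no reason is given for the difference.

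The fault is more than a missing detail. The plan does have a rule on prior medication, and that rule allows the home drug to continue. Staff who follow it would give study tamsulosin on top of a home alpha-blocker. The plan itself lists dizziness and asthenia among tamsulosin's adverse effects, and its stopping rule acts only after a patient reports one. What is at stake is avoidable duplicate exposure, mostly in the two weeks before surgery.

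**Working it through.** **1. Is there any rule on alpha-blockers?** The sections that could hold one are:

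| Section | Written rule | Alpha-blocker use addressed? |
|---|---|---|
| Inclusion Criteria | stent placement for stones or other conditions | no |
| Exclusion 1, 3d, 5 | LUTS, retention, pelvic pain | no; these are conditions, not drug use |
| Exclusion 3 (rest), 4 | anticholinergic contraindication and use | no |
| Screening: chart review | limited to what bears on the criteria | no; it need not look for the drug |
| Screening: medical history | taken before randomization | may reveal the drug; no action attached |
| Study Drug/Intervention | prior medication may continue | permits it |
| Safety and Monitoring | stop after side effects | only after the event |

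The prior-medication sentence cannot be wholly literal, because exclusion 4 already bars anticholinergics. That limit does not reach alpha-blockers.

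**2. Exposure.** From the documents: study dose 0.4 mg/day; 14 days before surgery plus 7 with the stent, 21 in all. Assumed: home tamsulosin dose *h*. The plan calls 0.4 mg the most commonly used dosing, but gives no home dose for any patient.

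Intake over *d* days = (0.4 + *h*) × *d*; ratio to study dose = (0.4 + *h*)/0.4.

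| *h* (mg/day) | Daily | 14 days before surgery | 7 stent days | 21 days | Ratio |
|---|---|---|---|---|---|
| 0 | 0.4 | 5.6 | 2.8 | 8.4 | 1 |
| 0.4 (assumed) | 0.8 | 11.2 | 5.6 | 16.8 | 2 |
| 0.8 (assumed upper value, no source in the documents) | 1.2 | 16.8 | 8.4 | 25.2 | 3 |

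These figures show exposure, not harm: the documents give no relation between dose and toxicity. For another alpha-blocker the issue is duplicate class exposure, and the milligram figures do not apply.

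**3. How many patients?** The documents give no share *p* of candidates on an alpha-blocker. Applied to all 106 planned patients, assumed shares give:

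| Assumed *p* | Affected, 106 × *p* | Otherwise eligible needed if users are excluded, 106/(1 − *p*) | Extra |
|---|---|---|---|
| 1% | 1.06, about 1 | 107.07, so 108 | 2 |
| 5% | 5.3, about 5 | 111.58, so 112 | 6 |
| 10% | 10.6, about 11 | 117.78, so 118 | 12 |

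For an amendment these are upper figures at each share. Enrolment on this regimen began on 29 October 2014 and the document is dated 17 July 2017; any patients enrolled in between are outside the amendment's reach.

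**4. Sample size.** The plan has no figure of its own on this point. Its calculation (4 points, SD 6.5, two-sided 0.05, power 0.80) reproduces: the t-test gives 42.43, rounded up to the stated 43 per arm. Excluding alpha-blocker users changes none of the stated inputs, and the target of 53 per arm stands.

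**The case against.** The strongest reply is that few such patients would get through, and those who did would be noticed. The plan describes tamsulosin as a treatment for LUTS, and the exclusions for LUTS, retention and prostatitis remove the conditions it most clearly links to prior use. The operating surgeons belong to the study team, the hospital pharmacy supplies the drugs, a full history comes before randomization, and tamsulosin is known to be in both arms. The evidence for prior use is also thin. The remark on common dosing explains the choice of study drugs, and the Statistical Analysis remark that both regimens are occasionally used explains why few withdrawals are expected. Neither says that candidates arrive on an alpha-blocker.

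Most of this stands as a limit on frequency. It does not remove the gap. No safeguard carries a rule on alpha-blockers, and a clinician who intervened would be departing from the one rule that exists. A patient who takes the drug for another reason, or who is not classed as having LUTS, remains eligible.

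Three stronger readings are tempting:

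- *The treatment comparison is biased.* Tamsulosin is in both arms and randomization should balance prior use, so no between-arm bias is expected. Effects through drop-outs or a more varied alpha-blocker background are speculative, and the Statistical Analysis section applies intent-to-treat to withdrawals.
- *Many patients will be double-dosed, or harmed.* The documents give neither a frequency nor a harm at the doubled dose.
- *All trial participants are exposed for 21 days.* This is true of the current regimen only; the 95 patients enrolled earlier were on the 7-day regimen.

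**Conclusion.** The point holds as a patient-safety and eligibility gap in the current regimen. A patient on an alpha-blocker who is not caught by the condition-based exclusions may be enrolled and told to continue it, receiving twice the study dose of tamsulosin if the home dose is 0.4 mg. That doubling rests on the assumed home dose; the permission rests on the text alone. How often it would happen cannot be estimated and is probably low. The change is worth making because it is cheap and the rule as written points the wrong way, not because the trial's result is in doubt. Consent form text was not available and nothing is inferred from it.

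**What to change.** For patients not yet enrolled:

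1. Extend exclusion 4 to current anticholinergic or alpha-blocker use.
2. Limit the prior-medication sentence in Study Drug/Intervention to medications other than these two classes.
3. Update the restated list in Patient Screening and Recruitment, so that the chart review covers alpha-blockers.
4. As optional tidying, add tamsulosin hypersensitivity to exclusion 3; clinicians would probably act on it anyway.

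The cost is a wording amendment, applied through the existing chart review and history, plus the loss of a small, unknown number of otherwise eligible patients. No new visit, unblinding or change to the analysis is needed.

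Stopping the home alpha-blocker instead would keep those patients, but should not be offered as cost-free. It changes care for the sake of the study, against the assurance in Safety and Monitoring that participation will not influence care. It may also affect the baseline USSQ, which is completed before study medication starts. The same section excludes patients who discontinue medications without saying which, so that wording would need clarifying too. Exclusion is the cleaner choice.
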